Exclusion criteria:	

- Age < 18 years

- Obvious pregnancy

- Known preexisting Do Not Attempt Resuscitation order

Study objectives:	Primary objective: To evaluate feasibility and defibrillation safety in a randomized pilot trial, comparing the effect of a double defibrillation strategy, initiated as soon as possible after the first shock has been delivered, among all patients with Out of Hospital Cardiac arrest (OHCA) remaining in a shockable rhythm (VT/VF) after the first defibrillation. The results from this pilot trial will inform design of a larger multicenter survival study.
	Secondary objective: To provide a power-calculation for a larger survival study
	Safety objective: To asses safety of an early DSD strategy in terms of CPR quality and defibrillation performance.
Study endpoints:	Primary endpoints are defined as feasibility and safety measures as described below:
	Feasibility:  - Number of EMS defibrillations prior to randomization (target > 80% before third defibrillation)  - Among patients randomized to DSD, proportion that received DSD (target > 80%)  - Among patients randomized to standard, proportion that received DSD (target < 10%)

Version No: 1.1

Date: 2024-10-27 12 (48)

- Proportion of eligible patients included and randomized (target > 80%)

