#### Performing DSD within the Double-D trial:

In this trial all patients will be connected to corpuls3 with electrodes in standard A - L electrode position.

If another defibrillator (AED) is already attached to the patient at EMS arrival the EMS will remove the electrodes from the other defibrillator and attach cor-patch electrodes in standard A-L position and connect them to corpuls3 in all cases. This is all part of current routine practice.

If randomized to intervention, electrodes from a second defibrillator (corpuls3 or corpuls1) are placed in the anterior-posterior position during interruptions in chest compressions for ventilation, thus not interfering with the electrodes from the first defibrillator. Attachment of the second defibrillator electrodes shall be made as soon as possible after randomization.

Version No: 1.1

Date: 2024-10-27 17 (48)

If the patient has VT/VF at the subsequent rhythm analysis (every two minutes during CPR) both defibrillators are charged simultaneously during chest compressions and shocks from the two defibrillators are delivered with approximately 1 second delay from each other (A-L first, A -P second when possible) and CPR immediately resumed (DSD strategy). For all consecutive defibrillations a DSD strategy will be used if the patient remains in VT/VF, termination of resuscitation or decision to transfer the patient to hospital. The total shock pause (hands off interval where no compressions are performed) is recommended to be less than 5 seconds.

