#### Feasibility:

- Number of EMS defibrillations prior to randomization (target > 80% before third defibrillation)
- Among patients randomized to DSD still in VF in the following rhythm analysis, proportion that received DSD (target > 80%)
- Among patients randomized to standard, proportion that received DSD (target < 10%)

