## 6.3. Subjects

#### 6.3.1. Inclusion criteria

- OHCA patients in VT/VF at rhythm analysis after ambulance arrival and at least one defibrillation performed in standard (A-L) position

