## 6.3.3. Investigation population

The goal is to include 40 patients (30 randomized to DSD and 10 to standard treatment). The 3:1 ratio was chosen since our main focus in this pilot study is the interventional treatment but also to evaluate the randomization process and adherence to protocol.

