# 6.6. Description of the clinical procedures and diagnostic methods relating to the clinical investigation

[figure not shown]
The study is conducted in the prehospital emergency medical services, i.e. ambulance organizations. The trial will be conducted by participating ambulance units attending OHCA's. These units will perform screening for inclusion, randomization, intervention or control treatment and initial follow-up. All ambulance units in Sweden follow European resuscitation council (ERC) guidelines published in 2021 [4] and perform team training on an annual basis for high quality provision of ACLS care in OHCA.

In clinical practice a cardiac arrest is confirmed by the absence of consciousness and absence of normal or no breathing. In this clinical situation cardiac arrest shall be suspected and CPR initiated. In all cases of OHCA a defibrillator should always be attached with the standard pad placement first (A-L position) in accordance with standard of care and ERC guidelines. If there is VT/VF or an AED suggests defibrillation, defibrillation should be performed, and immediate chest compressions resumed.

Thereafter, the patient can be screened for inclusion. If two defibrillators study specific defibrillators on site, and no exclusion criteria the patient can be included and randomized. Randomization will be performed by drawing a scratch-card with concealed allocation that will be stored with the EMS defibrillators. All scratch-cards will be pre-randomized in a 3:1 ratio in blocks consisting of 4-8-12 and stratified by region and ambulance provider.

Version No: 1.1

Date: 2024-10-27 28 (48)

OHCA = Out of Hospital Cardiac Arrest, VT/VF = pulseless Ventricular Tachycardia / Ventricular Fibrillation, CPR = Cardiopulmonary Resuscitation, DSD = Double Sequence Defibrillation, CRF = Clinical Report Form

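### The primary feasibility endpoint on DSD receipt has two denominators, all patients randomized to DSD in the synopsis and only those still in VF in section 6.2.1, and its verdict can depend on which is used

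*Protocol*

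**What the plan says.** The synopsis (Study endpoints) defines receipt of the intervention as "Among patients randomized to DSD, proportion that received DSD (target > 80" per cent). Section 6.2.1, under Feasibility, defines it as "Among patients randomized to DSD still in VF in the following rhythm analysis, proportion that received DSD (target > 80" per cent). The limit is the same and the denominator is not. Both bullets stand under primary endpoints.

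The control-arm bullet has the same denominator in both places: "Among patients randomized to standard, proportion that received DSD (target < 10" per cent).

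Three other sections decide who can receive DSD:
- Section 2.2 gives it conditionally: "If the patient has VT/VF at the subsequent rhythm analysis (every two minutes during CPR) both defibrillators are charged simultaneously".
- Section 6.3.1 admits "OHCA patients in VT/VF at rhythm analysis after ambulance arrival and at least one defibrillation performed in standard (A-L) position", which does not require the arrhythmia to persist after that shock.
- Section 6.6 describes the first shock and resumed compressions, and then says "Thereafter, the patient can be screened for inclusion".

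On size, section 6.3.3 states: "The goal is to include 40 patients (30 randomized to DSD and 10 to standard treatment").

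**The concern.** A patient allocated to DSD who is out of VT/VF at the next analysis, and stays out, is not due a double shock. Withholding it follows the protocol. On the synopsis definition that patient is in the denominator, cannot enter the numerator and counts as non-adherent. On the 6.2.1 definition the patient is left out. One data set can therefore meet the target under one section and miss it under the other, and the sponsor would have to choose after seeing the results.

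There is also a smaller wording gap. The 6.2.1 restriction names VF only, while the intervention is triggered by VT or VF. Read literally, a patient in pulseless VT at the next analysis is due DSD but falls outside the endpoint.

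The control bullet raises a question of information only. A control with no shock after randomization had no occasion to cross over. Such controls are properly counted as treated as assigned, but they add nothing to what the pilot learns about crossover.

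**Working it through.** **Arm sizes.** 40 × 3/4 = 30 DSD and 40 × 1/4 = 10 standard, which reproduces section 6.3.3.

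**DSD receipt.** Let m be the number of the 30 DSD patients in VT/VF at the following analysis, and r the number of those who receive DSD. For simplicity, assume nobody else in the arm receives it. The synopsis proportion is r/30 and the 6.2.1 proportion is r/m. The protocol gives no value for m, so the values below are assumptions.

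On the synopsis definition, 24/30 = 80.0% is not above 80% and 25/30 = 83.3% is. So r must be at least 25, whatever m is.

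| m (assumed) | Synopsis result at perfect adherence, m/30 | 6.2.1 result at perfect adherence | Smallest r meeting the synopsis target | Smallest r meeting the 6.2.1 target |
|---|---|---|---|---|
| 30 | 100% | 100% | 25 | 25 (25/30 = 83.3%) |
| 27 | 90.0% | 100% | 25 (25/27 = 92.6% of those due DSD) | 22 (22/27 = 81.5%) |
| 25 | 83.3% | 100% | 25 (all of them) | 21 (21/25 = 84.0%) |
| 24 | 80.0% | 100% | cannot be met | 20 (20/24 = 83.3%) |
| 18 | 60.0% | 100% | cannot be met | 15 (15/18 = 83.3%) |

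The definitions agree only when m = 30. With m = 27, any r from 22 to 24 meets the target in 6.2.1 and misses it in the synopsis. With m = 24 or fewer, no level of adherence meets the synopsis target.

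The simplification has a limit. A patient out of VT/VF at the following analysis who re-fibrillates later and then receives DSD would enter the synopsis numerator but not the 6.2.1 proportion. This narrows the gap for such patients without removing the contradiction.

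**Control crossover.** With 10 controls, 1/10 = 10.0% is not below 10%, so only zero crossovers meets the target. If 7 of the 10 were shocked after randomization (assumed), 1/7 = 14.3% also fails, and again only zero passes. The met or not-met result is therefore the same on either denominator.

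The information behind a zero does differ. The exact two-sided 95% upper limit for 0/n is 1 − 0.025^(1/n):
- 0/10: 1 − 0.025^(1/10) = 30.8%
- 0/7: 1 − 0.025^(1/7) = 41.0%

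**The case against.** **The synopsis is only a summary, and a reader can take 6.2.1 as governing.** In practice that may happen. But the protocol does not say that the body prevails, and the synopsis bullet is a complete definition with its own numerical limit.

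**Section 7.1 makes intention to treat the principal analysis, which favours all randomized patients.** That principle protects the comparison of outcomes between arms. The receipt bullet is a one-arm description of adherence. Showing the all-randomized count beside it keeps the full picture.

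**Few randomized patients may be free of VT/VF.** Section 6.1 describes patients in VT/VF after the first shock, which would push m towards 30. Section 6.6 relies on a flow-chart that is not shown in the text at hand, so the order of rhythm check and randomization cannot be settled. This stands as a limit on size. The restriction in 6.2.1 nevertheless implies that some DSD patients are expected not to be in VF.

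**Stronger readings that a reader might infer.** One is that the control bullet is itself defective because controls who need no shock count as adherent, making its target too easy. The documents do not support this. Those controls were treated as assigned, the bullet is identical in both places, its denominator fits section 7.1, and with 10 controls only zero crossovers passes either way. Another is that mismatched denominators would leave the survival study too small, since a synopsis objective is "To provide a power-calculation for a larger survival study". Section 7.4 says only that pilot results will inform that calculation. Nothing in the protocol subtracts these two proportions or scales the main study by their difference.

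**Conclusion.** The contradiction on DSD receipt is real and can be read directly from the text. It can reverse the verdict on one of the listed primary feasibility targets: with 24 of 30 DSD patients in VT/VF (assumed), perfect adherence reads 80% and misses in the synopsis, against 100% in 6.2.1. How likely a reversal is depends on a share that the protocol does not give.

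The control target is sound as written. The useful addition is to show how many controls had an occasion to cross over, because a zero count excludes less when it rests on fewer such patients (upper limit 41% for an assumed 7, against 31% for all 10). This has no effect on whether the target is met with 10 controls, and no effect on main-study size should be claimed.

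Severity is minor. Section 6.2.1 names the proportion randomized before three EMS defibrillations as the main feasibility endpoint, the targets are descriptive, and the protocol attaches no go/no-go rule to them.

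**What to change.** 1. Use one definition of DSD receipt in the synopsis and in 6.2.1, for example: *of patients randomized to DSD who are in VT/VF at the rhythm analysis following randomization, the share given DSD (target above 80%)*. Write VT/VF in both places.
2. Beside it, show how many of all patients randomized to DSD received it. This also captures DSD given after a later recurrence.
3. Do not resolve the conflict by moving receipt to all randomized patients with the 80% limit kept. That would make correct treatment count against the target in both sections.
4. Leave the control target on all randomized controls, below 10%. Beside it, report crossovers among controls with at least one shock after randomization. Any control given DSD has by definition been shocked, so no crossover drops out.

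The cost is a small wording amendment under section 9, with authority approval if it is judged substantial. Shocks after randomization should be derivable from CRF1, which records shocks before randomization and electrode placement for each defibrillation. Rhythm at each analysis is not among the listed CRF1 items and would have to be read from the exported defibrillator files, but 6.2.1 as written already needs this. The restricted proportions rest on fewer patients and are less precise, which the report should say. If enrolment has begun, date the change and state whether any receipt or crossover data were already known.

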#### Safety:

- Major adverse events (e.g. DD, skin burns)
- Chest compression fraction (hands off time during CPR, target > 80% in both groups)

#### 6.2.2. Secondary endpoint (s)

- Proportion of patients receiving sustained return of spontaneous circulation (ROSC)
- Number of defibrillations to sustained ROSC

#### 6.2.3. Tertiary endpoints

- Survival to hospital admission
- Survival to hospital discharge
- Survival at 30 days
- Neurological function (mRS and CPC) at 30 days
- Neurological function (mRS and CPC) and Health-related Quality of life at 90 days
- Neurological function (mRS and CPC) and Health-related Quality of life at 180 days

Version No: 1.1

Date: 2024-10-27 26 (48)

The tertiary outcomes were chosen to comply with the "Core Outcome Set for Cardiac Arrest in Adults" advisory statement From the International Liaison Committee on Resuscitation.[13]

#### 6.2.1. Description of the intervention

Please see 6.6

## 6.2.1. Description of the comparator

Please see 6.6. Standard defibrillation with Corpatch electrodes in the A-L position using one corpuls3 defibrillator (routine clinical praxis)

## 6.3. Subjects

#### 6.3.1. Inclusion criteria

- OHCA patients in VT/VF at rhythm analysis after ambulance arrival and at least one defibrillation performed in standard (A-L) position

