**Study rationale:** In order to evaluate if an early DSD-strategy could benefit all patients with VT/VF after the first shock, including those not in refractory VF the Double D trial is designed. The first phase of the Double D trial is a pilot-study assessing feasibility and defibrillation safety, presented here. If DSD would prove to be superior to standard defibrillation in a broader cardiac arrest population, also among those not in refractory VF, this would have a large impact on how Advanced Cardiac Life Support (ACLS) should be performed.

**Design:** This is an academic, investigator initiated, openlabel pilot study with a randomized controlled trial (RCT) design and 3:1 allocation (3 DSD: 1 standard). Screening for inclusion will be performed in all cardiac arrests by participating EMS units where there are two study-specific defibrillators available on site (One (1) Corpuls3 + one (1) Corpuls3).

**Study population:** All OHCA patients (≥18 years) with VT/VF at rhythm analysis, at least one defibrillation performed in standard A-L position.

**P:** Adult patients, 18 years or older, with OHCA and a shockable rhythm (VT/VF) after ambulance arrival and at least one defibrillation in standard position

**I:** Application of a second defibrillator with pad-placement in the anterior-posterior (A-P) position as early as possible after the first shock and a double sequential defibrillation in the following rhythm analysis phase if the patient is still in VT/VF

**C:** Standard defibrillation electrode placement (A-L)

**O**: Assessment of feasibility in terms of inclusion, time to inclusion and randomization, adherence to protocol and safety in terms of adverse events and CPR quality.

The pilot study is conducted in the prehospital emergency medical services, i.e. ambulance organizations primary in Alingsås/Kungälv, Sahlgrenska, Gothenburg and Region Halland. Other areas/regions can be allocated later.

Version No: 1.1

Date: 2024-10-27 11 (48)

	The trial will be conducted by participating ambulance units attending OHCA's. These units will perform screening for inclusion, randomization, intervention or control treatment and initial follow up.
Investigational device:	Corpuls3
Number of subjects:	40
Inclusion criteria:	- OHCA patients with VT/VF and at least one (1) defibrillation performed in standard (A-L) position

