## 5. Objectives and hypotheses of the clinical investigation

## 5.1. Objectives

## 5.2.1. **Primary objective**

The overall aim of this pilot study is to evaluate feasibility of a Randomized Controlled Trial comparing a strategy with DSD defibrillation as soon as possible to standard defibrillation in OHCA patients who remain in VT/VF after the first shock.

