## 6. Design of the clinical investigation

#### 6.1. General information

**Design:** This is an academic, investigator initiated, open-label pilot study with a randomized controlled trial (RCT) design and 3:1 allocation (3 DSD: 1 standard). Screening for inclusion will be performed in all cardiac arrests by participating EMS units where there are two study-specific defibrillators available on site (One (1) Corpuls3 + one (1) Corpuls3 *or* one (1) Corpuls1).

**Study population:** All adult OHCA patients (≥18 years) with VT/VF at rhythm analysis after the first defibrillation.

Version No: 1.1

Date: 2024-10-27 25 (48)

**Study setting:** The study is conducted in the prehospital emergency medical services, i.e. ambulance organizations. The trial will be conducted by participating ambulance units attending OHCA's staffed with special nurses. These units will perform screening for inclusion, randomization, intervention or control treatment and initial follow-up. All ambulance units in Sweden follow European resuscitation council (ERC) guidelines published in 2021 [4] and perform team training on an annual basis for high quality provision of ACLS care in OHCA.

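### The objective and section 6.1 define patients still in VT/VF after the first shock, but the enrolment steps let patients be randomised before that rhythm is checked, so part of the randomised set can fall outside the stated population

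*Protocol*

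**What the plan says.** Three places in the protocol define the population by persistence of VT/VF:

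- Synopsis, primary objective: patients "remaining in a shockable rhythm (VT/VF) after the first defibrillation".
- Section 5.2.1, primary objective: "OHCA patients who remain in VT/VF after the first shock".
- Section 6.1, study population: adults "with VT/VF at rhythm analysis after the first defibrillation".

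Two places do not clearly require persistence:

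- Synopsis, study population: patients "with VT/VF at rhythm analysis, at least one defibrillation performed in standard A-L position".
- Section 6.3.1, inclusion criterion: "OHCA patients in VT/VF at rhythm analysis after ambulance arrival and at least one defibrillation performed in standard (A-L) position".

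The order of events is set out in section 6.6. For VT/VF, "defibrillation should be performed, and immediate chest compressions resumed". Then: "Thereafter, the patient can be screened for inclusion". The conditions named at that point are two study defibrillators on site and no exclusion criterion, after which the scratch-card is drawn. The rhythm is read again only later. In section 2.2, DSD is given "If the patient has VT/VF at the subsequent rhythm analysis", with analyses every two minutes, and the synopsis description of the intervention makes the same condition.

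The primary adherence endpoint appears in two forms with the same target of more than 80%. The synopsis counts all patients randomised to DSD. Section 6.2.1 counts only those still in VF at the following analysis. Section 7.1 makes intention to treat over all randomised patients the principal analysis and adds an mITT that removes patients not in VT/VF, without saying at which analysis.

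**The concern.** A patient who has converted by the check after the first shock is outside the population of sections 5.2.1 and 6.1, yet can be randomised under section 6.6. At that check neither arm's shock strategy applies to such a patient. Crews who read the protocol differently would enrol different patients at different moments.

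Three things are at stake: which population the clinical estimates describe, when section 7.4 says the results will inform the main study's sample size; whether a primary feasibility target is judged met or failed; and who drops out of the mITT.

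**Working it through.** **Step 1: do the passages conflict?** Under section 6.1, VT/VF must be present at an analysis after the first shock. Under section 6.6 the sequence is shock, compressions, screening, card, next analysis. For a patient enrolled straight after the first shock, the rhythm that section 6.1 requires is not yet known when the card is drawn. Criterion 6.3.1 fits either order and does not settle it. The section 6.2.1 adherence denominator supports this reading: limiting it to patients still in VF is needed only if some randomised patients no longer are.

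**Step 2: inputs.** From the protocol: 40 patients, 30 DSD and 10 standard (section 6.3.3; 40 × 3/4 = 30, 40 × 1/4 = 10); adherence target above 80% (synopsis and section 6.2.1). Assumed: c, the share of randomised patients not in VT/VF at the first analysis after randomisation. The protocol gives no value, so a range is shown. The protocol has no sample size derivation to reproduce.

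**Step 3: adherence target.** More than 80% of 30 means more than 24, so at least 25. Suppose every DSD patient still in VT/VF receives DSD and converted patients do not re-fibrillate. On the synopsis denominator the number receiving DSD is then binomial with n = 30 and probability 1 − c. On the section 6.2.1 denominator, adherence is 100% whatever c is.

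| Assumed c | Expected synopsis adherence | Chance of at least 25/30 |
|---|---|---|
| 10% | 90% | 93% |
| 20% | 80% | 43% |
| 30% | 70% | 8% |
| 40% | 60% | 0.6% |

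**Step 4: clinical contrasts.** Suppose c is equal in both arms, allocation has no effect in converted patients, and the risk difference is d among those still in VT/VF. The intention-to-treat risk difference is then (1 − c) × d: 0.8d at c = 20%, 0.6d at 40%, 0.4d at 60%. This applies to proportions such as ROSC and survival. Shock counts and odds ratios are attenuated too, but not by exactly this factor.

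**Step 5: patients still in VT/VF at that check.** DSD: 30 × (1 − c). Control: 10 × (1 − c). This gives 24 and 8 at c = 20%, 21 and 7 at 30%, 18 and 6 at 40%, and 12 and 4 at 60%.

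**The case against.** The strongest reply is that this is loose wording in a protocol that plainly expects randomisation during CPR, in keeping with an early strategy. The section 6.2.1 denominator and the mITT already allow for converted patients, and the flow-chart that section 6.6 says inclusion will follow is not shown in the text available. Screening could also be taken to mean applying criterion 6.3.1 in its stricter sense. This is why the point rests on the conflict between sections and not on 6.3.1 alone. It does not remove the conflict, and it leaves two adherence denominators in one protocol.

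Several stronger inferences are tempting but not supported:

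- **That every arm comparison is diluted.** The main feasibility endpoint is a single proportion over all included patients. The section 6.2.1 adherence endpoint is already conditioned on rhythm. Chest compression fraction can differ whatever the rhythm, because the second pads are applied soon after randomisation.
- **That the stricter reading would remove all dilution.** If crews waited for the analysis after the first shock, another shock would normally fall due at that check, and some patients would convert on it before their first assigned shock.
- **That every enrolment precedes the rhythm check.** Section 6.6 lets patients be included when a second defibrillator arrives later. Some of them will already have documented VT/VF after the first shock.
- **That the pilot loses power, or the main study would be mis-sized by a known factor.** Section 7.4 plans no power calculation and no hypothesis test, and neither c nor the event rates are given. If the main study enrols in the same way, the all-randomised contrast is itself the relevant one to plan on.

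Re-fibrillation also matters. DSD applies to later shocks, so a patient converted at the first check may still receive it. The table and the (1 − c) factor are therefore upper bounds on the effect of a given c.

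**Conclusion.** The point stands as an inconsistency with two practical consequences. First, the intention-to-treat clinical contrasts (ROSC, shocks to ROSC, survival, neurological outcome) describe a broader population than the objective and are attenuated by an unknown amount, some of which would remain under either reading. Second, the synopsis adherence target depends on conversion as well as on crew behaviour. On an assumed c of 20% to 30% it would be met with probability of only about 43% to 8% under perfect adherence, while the section 6.2.1 version is unaffected by c. The feasibility conclusion could therefore turn on which section is followed. These figures rest on the assumed c, on no re-fibrillation, and on exactly 30 DSD patients. The conflict between sections does not depend on them. It should be resolved, but it does not invalidate the pilot.

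**What to change.** 1. Reconcile the synopsis (population, inclusion criterion and objective) and sections 5.2.1, 6.1, 6.3.1 and 6.6 to one population and one randomisation moment, naming the rhythm analysis that qualifies a patient. If randomisation stays before the next rhythm check, restate the objective population as patients with at least one A-L shock for VT/VF.
2. Use the section 6.2.1 denominator for DSD adherence in the synopsis as well.
3. In section 7.1, state which rhythm analysis defines the mITT exclusion for not being in VT/VF, and apply it identically in both arms.
4. Beside the intention-to-treat result, report by arm the share still in VT/VF at the first analysis after randomisation, and the clinical outcomes in that group. Read the rhythm from the defibrillator ECG files that section 8.1 already has exported.

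The cost is wording in several places and one table. The subgroup must be labelled descriptive: at an assumed c of 30% to 60% it holds only 7 to 4 controls. Section 7.6 plans no exploratory or sensitivity analyses because of the small sample, so it should mention this summary. The group is also not perfectly protected from allocation, since section 4.3 notes that placing the posterior pad briefly interrupts compressions in the DSD arm, and this can happen before the check.
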